### **2.2 Research Hypothesis**

The primary hypothesis in this study is that the radiotherapy combined with best supportive care (RT+BSC) will have a greater clinical improvement of an index symptom of pain or abdominal discomfort compared to best supportive care alone (BSC) in patients with symptomatic hepatocellular carcinoma (HCC) or liver metastases.

### **2.3 Study Design**

CCTG HE.1 is a multi-center, open-label, randomized phase III trial which randomizes patients with end-stage, painful, symptomatic hepatocellular carcinoma (HCC) or liver metastases to receive RT+BSC or BSC after stratification by center and type of liver cancer (HCC vs. liver metastases).

This study was activated on July 23, 2015. The final analysis would be performed when 45 evaluable patients are available for analysis, which would be achieved after approximately 65 patients are randomized with an assumption of 25% drop out rate. The 66th patient was randomized on June 2, 2022, however, after a review, only 42 patients were evaluable from the 66 randomized patients. Because of the slow accrual, after consulting with the CCTG Data Safety Monitoring Committee (DSMC), the trial

committee decided to close the accrual on June 2, 2022, with the last expected date for the collection of trial data from all 66 randomized patients as September 8, 2022, which is therefore defined as the data cut-off date for final analysis. The final analysis will be performed after all data observed on or before this date are received and cleaned. This analysis plan describes the analyses performed for the final analysis.

The CCTG DSMC has been reviewing safety data every six months (usually at the time of the bi-annual CCTG Spring and Fall meetings) and as otherwise required. These analyses have been prepared by a CCTG/Queen's Senior Biostatistician.

### **3. Objectives**

#### **3.1 Primary**

The primary objective of this study is to determine if patients with symptomatic liver tumours (either HCC or liver metastases) who undergo best supportive care (BSC) plus a single 8 Gy fraction of radiation therapy to the liver experience a significant improvement in symptoms (defined as a  $\geq 2$  point decrease in their pain 'intensity at worst' score on BPI) from baseline to 30 days as compared to patients receiving BSC alone.

#### **3.2 Secondary**

Secondary objectives are to compare the two treatment arms with respect to:

- Proportion of patients experiencing grade  $\geq 2$  adverse events at 30 days and 90 days.
- Proportion of patients alive at 90 days.
- Proportion of patients achieving improvement of liver cancer pain/discomfort by  $\geq 2$  points from baseline to day 30 and day 90 in all BPI pain scores.
- Proportion of patients reporting clinically significant improvement in QoL from baseline to day 30 and day 90 as defined by a  $\geq 5$  point change in the Functional Assessment of Cancer Therapy (FACT) Hepatobiliary Subscale (FACT-HBS) and Trial Outcome Index (FACT-TOI).
- Proportion of patients achieving a 25% reduction in opioid use at 30 days (employing daily morphine equivalence).

### **4. Endpoints**

#### **4.1 Primary Efficacy**

The primary efficacy endpoint is proportion of patients achieving improvement of liver cancer/discomfort by  $\geq 2$  points in pain 'intensity at worst' on BPI from baseline to day 30.

#### **4.2 Secondary Efficacy**

The secondary efficacy endpoints are:

- Proportion of patients experiencing grade  $\geq 2$  adverse events at day 30 and day 90.
- Proportion of patients alive at day 90.

- Proportion of patients achieving improvement of liver cancer pain/discomfort by  $\geq 2$  points from baseline to day 30 and day 90 in all BPI pain scores.
- Proportion of patients reporting clinically significant improvement in QoL from baseline to day 30 and day 90 as defined by a  $\geq 5$  point change in the Functional Assessment of Cancer Therapy (FACT) Hepatobiliary Subscale (FACT-HBS) and Trial Outcome Index (FACT-TOI).
- Proportion of patients achieving a 25% reduction in opioid use at 30 days (employing daily morphine equivalence scale).
- Proportion of patients achieving improvement of liver cancer pain/discomfort by  $\geq 2$  points in pain ‘intensity at worst’ AND with no increase in opioid use (employing daily morphine equivalence scale) on BPI from baseline to 30 days.

#### **4.3 Safety**

The safety endpoints are serious and non-serious adverse events (clinical and laboratory), laboratory parameters.

### **5. Sample Size and Power**

The primary objective of this study was to determine a single 8 Gy dose of RT with best supportive care (BSC) would show an improvement of  $\geq 2$  points in pain ‘intensity at worst’ on the Brief Pain Inventory (BPI) from baseline to day 30 relative to BSC alone in patients with painful liver tumours (either HCC or liver metastases). 45 evaluable patients with BPI at baseline and at day 30 were required to detect a change in proportion of patients with a significant improvement in BPI from 5% (no radiation) to 40% (with radiation therapy) with 80% power and two-sided 0.05 level. With 42 evaluable patients included in the final analysis, the study would have 77% power to detect the significant improvement in BPI from 5% (no radiation) to 40% (with radiation therapy) at two-sided 0.05 level or 80% power to detect the significant improvement in BPI from 5% (no radiation) to 42% (with radiation therapy) at two-sided 0.05 level.

### **6. Data Set Descriptions**

Two types of analysis samples will be used:

All Randomized Patients:

All patients who have been randomized in the study with the treatment arm being as randomized.

All Treated Patients:

All patients who are randomized to RT+BSC arm and have received a single 8 Gy dose of RT and all patients who are randomized to BSC arm.

All Day 30 BPI Response Evaluable Patients:

All patients who have completed a baseline and 30 days follow-up BPI.

All Day 90 BPI Response Evaluable Patients:

All patients who have completed a baseline and a day 90 follow-up BPI.

All BPI Response from Day 30 to Day 90 Evaluable Patients:

All patients who have randomized to BSC arm and crossed over to RT+BSC arm after their day 30 assessment and also completed their day 30 and day 90 BPI.

All QoL (quality of life) Evaluable Patients:

All patients who have completed the quality of life questionnaire at baseline and on days 30 and 90.

All Change in Opioid Evaluable Patients:

All patients who have completed Pain/Discomfort and Medication Questionnaires at baseline and within 24 hours of the 30 day visit.

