8.1 Best Supportive Care (Arms 1 and 2)

Patients on both treatment arms will receive BSC, with analgesia as needed and palliative care/pain specialist involvement in their care (per local policy). The treating team will determine the most appropriate interventions for individual patients. In general, analgesia strategies that may be considered include:

- Opioids: Short-acting hydromorphone q 2-4 hours prn is the opioid of choice with the dose individualized and titrated to maximize pain relief effect and minimize side effects. A longer interval between dosing may be needed for patients with more impaired liver function. Long acting hydromorphone may also be used if around-the-clock pain relief is required. The pharmacokinetics of fentanyl and methadone are not significantly affected by hepatic impairment, so they are alternatives in the setting of liver failure [Smith 2009]. Other opioids are also permitted;
- Steroids: Dexamethasone is sometimes useful in these patients. If patients are on dexamethasone, it is recommended that they stay on the same dose for at least 3 days before entering the trial with no plans for altering the dose during the first month of the study, if clinically suitable. Note that even if patients are taking regular steroids, anti-emetics one hour prior to RT delivery, including a steroid, should be delivered (see section 8.3.1); and,
- Acetaminophen: 325 mg to 1 g q 4 hours, up to 3 g per day.

It is recommended that patients bring their pain medication pill bottles to each follow-up appointment and that the study nurse or CRA review the medication table completed by the patient (in Part Two of the Pain/Discomfort and Medication Questionnaire). All changes in pain medication, including steroid and over the counter analgesia, should be recorded.

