10.0 CRITERIA FOR MEASUREMENT OF STUDY ENDPOINTS

10.1 Definitions

10.1.1 Evaluable for adverse events. All patients will be evaluable for adverse event evaluation from the time of randomization.

10.1.2 Evaluable for BPI response. All patients who have completed a baseline and 30 days follow-up BPI will be considered evaluable for the primary endpoint. Patients who complete a baseline and a day 90 follow-up BPI will be considered evaluable for secondary BPI endpoints. Patients from Arm 1 who cross over to Arm 2 after their day 30 assessment are evaluable for BPI response from day 30 to day 90, if they have completed their day 30 and day 90 BPI.

10.1.3 Evaluable for quality of life assessment. All patients who have completed the quality of life questionnaire at baseline and on days 30 and 90 are evaluable for the quality of life endpoint.

10.1.4 Evaluable for change in opioid analysis. All patients who have completed Pain/Discomfort and Medication Questionnaires at baseline and within 24 hours of the 30 day visit are eligible for assessment. Only analgesic use in the past 24 hours will be recorded to increase compliance. If the patient is too unwell to visit the clinic, the Pain/Discomfort and Medication Questionnaire can be completed by the study nurse following a telephone call to the patient. Note: large fluctuations in opioid use are unlikely to occur due to intolerability of medications for many patients.

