14.2 Endpoints and Analysis

A stratified Cochran–Mantel–Haenszel (CMH) test adjusting for the stratification factor (HCC versus liver metastases) will be used to compare between two treatment arms for binary endpoints, such as proportion of patients with symptomatic HCC or liver metastases who report an improvement in pain/discomfort "intensity at worst" on BPI from baseline to day 30, proportion of patients with a clinically significant favourable change from baseline to day 30 and day 90 in other BPI scores, QoL on FACT-HBP, TOI and FACT-Hep and subscales, and proportion of patients with a 25% reduction in opioid use at 30 days. Primary analysis will include all patients who are assessed at both baseline and follow-up time of interest. Sensitivity analysis will also be performed by including those without assessment at specific follow-up time in the "no improvement" group. As cross-over of control patients to the RT Arm is permitted after day 30, after the primary endpoint (change in BPI on average) is assessed, the proportion of crossover patients who have RT at day 30 who have a subsequent clinically significant improvement in BPI at day 90 will be reported. The stratified logrank test will be used for time-to-event outcomes such as survival. A subgroup analysis will be performed based on the location of the metastases (HCC versus liver).

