## 7. Statistical Analysis

### 7.1 General Methods

All comparisons between treatment arms will be carried out using a two-sided test at an alpha level of 5% unless otherwise specified.

When appropriate, discrete variables are summarized with the number and proportion of subjects falling into each category, and compared using Fisher's exact test. Continuous and ordinal categorical variables are summarized using the mean, median, standard error, minimum and maximum values and when appropriate, compared using the Wilcoxon test.

Percentages given in the summary tables will be rounded and may therefore not always add up to exactly 100%. Listings, tabulations, and statistical analyses will be carried out using the SAS (Statistical Analysis System, SAS Institute, North Carolina, USA) software.

Unless otherwise specified, date of randomization and stratification factors will be taken from the Centralized Randomization File.

Baseline evaluations will be those collected on CRF Eligibility Worksheet and Baseline Report and closest to, but no later than, the first day of study treatment for treated subjects and closest to, but no later than, the date of randomization, for subjects who were randomized but who never received treatment.

Laboratory results, adverse events, and other symptoms are coded and graded using the CTCAE Version 4.0 Criteria.

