### 7.6 Safety

#### 7.6.1 Adverse Events

Adverse events are assessed using the NCI Common Terminology Criteria for Adverse Events (CTCAE) v4.0 handbook and those with grade 2 or higher are recorded on the baseline report, 30 day follow-up report, and 90 day follow-up report. Events reported on 30 day follow-up report will be summarized respectively for patients who were randomized to RT+BSC arm and received radiotherapy and who were randomized to BSC. Events reported on 30 day follow-up report will be summarized by the following three groups: (1) patients who were randomized to RT+BSC arm and received radiotherapy; (2) patients who were randomized to BSC and crossed over to RT+BSC; (3) patients who were randomized to BSC but not crossed over to RT+BSC.

Radiotherapy related adverse events are those events with a relation to protocol therapy of 3=possible, 4=probable or 5=definite.

Severe adverse events are those events reported with a CTCAE Grade of 3 or higher.

- Grade 2 or higher adverse events at days 30 and days 90: CTCAE grade per patient (**Table 29**)
- Grade 2 or higher radiotherapy related adverse events at days 30 and days 90: CTCAE grade per patient (**Table 31**)
- Severe adverse events at days 30 and 90: CTCAE grade per patient (**Table 32**)

Proportions of patients experiencing any grade  $\geq 2$  adverse event at day 30 and day 90 will be compared between treatment arms is conducted by a stratified CMH test (**Table 30**).

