**Table 30: Proportion of Patients with Grade  $\geq 2$  Adverse Event at Day 30 and Day 90**

	All Treated Patients		
	RT+BSC	BSC	CMH P-value (*)
Any Grade $\geq 2$ Adverse Event at Day 30	** (**.**)	** (**.**)	0.***
Any Grade $\geq 2$ Adverse Event at Day 90	** (**.**)	** (**.**)	0.***

\* Stratified Cochran-Mantel-Haenszel test adjusting for the stratification factor (HCC versus liver metastases)

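### The between-arm adverse event test (SAP Table 30) excludes unirradiated patients from the RT+BSC arm only, so it may not compare the arms as randomised

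*SAP*

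**What the plan says.** SAP section 6 defines the All Treated set as patients "randomized to RT+BSC arm and have received a single 8 Gy dose of RT and all patients who are randomized to BSC arm". An RT+BSC patient must have been irradiated to count; a BSC patient need only have been randomised.

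SAP 7.6.1 uses the same split for its day-30 summaries, which cover "patients who were randomized to RT+BSC arm and received radiotherapy and who were randomized to BSC". It then says that the proportions with any grade 2 or higher event "will be compared between treatment arms is conducted by a stratified CMH test". That sentence names no analysis set, but the header of Table 30, where the test is reported, does: "All Treated Patients". The endpoint is a secondary objective comparing the two arms (Protocol 1.2) and a listed secondary endpoint (SAP 4.2).

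The protocol sets no such condition. Section 10.1.1 states: "All patients will be evaluable for adverse event evaluation from the time of randomization". Section 14.2, on binary endpoints, states: "Primary analysis will include all patients who are assessed at both baseline and follow-up time of interest". It does not list adverse events among its examples, and its restriction concerns assessment, not receipt of radiotherapy. Section 7.3 has all randomised patients followed for 90 days.

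**The concern.** The set treats the two arms differently. Protocol 8.1 says that "Patients on both treatment arms will receive BSC", so an RT+BSC patient who misses radiotherapy is still due the care that qualifies every BSC patient for the set. That patient is dropped; the BSC counterpart stays.

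The reasons for missing radiotherapy may also bear on the outcome. Radiotherapy is planned within 5 working days after randomisation (SAP 7.4), and Table 1 lists progressive disease, intercurrent illness, adverse events and death among the reasons for not receiving it. A patient who deteriorates in that window leaves the RT+BSC arm, while a similar BSC patient remains. If those excluded are sicker than average, radiotherapy looks safer than it is, an unwelcome direction for a harm endpoint. If they have fewer recorded events, the bias runs the other way.

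The plan anticipates such patients: SAP 7.1 has a baseline rule "for subjects who were randomized but who never received treatment", and Table 1 has rows for them. Neither shows that there were any.

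**Working it through.** The documents give no figure for this comparison, so there is nothing to reproduce. The calculation below only illustrates how much the filter could matter.

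**Inputs from the documents**
- 66 patients randomised (SAP 2.3), allocated 1:1 (Protocol 4.2), taken as 33 per arm. Actual arm sizes are not given.
- Two-sided 5% test (SAP 7.1).

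**Assumptions, none given in the documents**
- k = RT+BSC patients not irradiated: 1 to 5.
- p = event rate in irradiated RT+BSC patients: 40% or 60%.
- e = event rate in the excluded patients: 0% to 100%, in steps of 1 point.

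**Shift in the RT+BSC rate.** The as-randomised rate is [p(33 − k) + k·e]/33 and the All Treated rate is p, so the shift (All Treated minus as-randomised) is k(p − e)/33. A negative shift makes radiotherapy look safer.

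| k | p = 40%, e = 100% | p = 40%, e = 0% | p = 60%, e = 100% | p = 60%, e = 0% |
|---|---|---|---|---|
| 1 | −1.8 points | +1.2 | −1.2 | +1.8 |
| 3 | −5.5 | +3.6 | −3.6 | +5.5 |
| 5 | −9.1 | +6.1 | −6.1 | +9.1 |

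For example, with k = 5, p = 40% and e = 100%, the shift is 5 × (0.40 − 1.00)/33 = −9.1 points. When e = p the shift is zero. For scale, the standard error of the difference with 33 per arm is √(2 × 0.6 × 0.4/33) = 12.1 points.

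**False-positive rate.** The true BSC rate is set equal to the as-randomised RT+BSC rate, so there is no true difference. All outcomes with 33 − k and 33 patients are enumerated, and the null is rejected when the single-stratum CMH statistic exceeds 3.84. The ranges are over p and e.

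| k | False-positive rate | Value when e = p (no bias) |
|---|---|---|
| 0 | 5.6% | 5.6% |
| 1 | 4.6% to 4.8% | 4.6% |
| 2 | 5.7% to 6.6% | 5.7% |
| 3 | 4.7% to 6.7% | 4.7% |
| 4 | 5.3% to 9.2% | 5.3% |
| 5 | 4.9% to 10.9% | 4.9% |

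The last column shows that part of the movement comes from the discreteness of small samples. The bias is the rise within a row. If the excluded patients' rate is only 20 points from that of the irradiated, the shift at k = 5 is 5 × 0.20/33 = 3.0 points, and the false-positive rate stays at or below 5.9% for every k from 1 to 5.

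**Two-stratum check.** With strata of 16 and 17 per arm, equal rates in both strata and e in steps of 20 points, the picture is the same: 5.4% for k = 0, 4.7% to 4.9% for k = 1, 4.8% to 6.9% for k = 3 and 4.9% to 10.6% for k = 5.

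**The case against.** The strongest reply is that no passage shows that any RT+BSC patient went unirradiated; Table 1 is an empty shell. That is correct, and the finding is conditional for that reason. Nor is the 10.9% typical: it needs 5 of 33 exclusions and a rate of 100% against 40%, or 0% against 60%. Even the largest shift is below the standard error of the difference.

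It can also be said that Protocol 10.1.1 defines who is evaluable and does not name a set for a between-arm test, and that 14.2 itself conditions on something after randomisation, namely being assessed. Both points are fair. But evaluability of all patients from randomisation does not fit a radiotherapy filter, and the condition in 14.2 applies to both arms alike.

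A treated-patient set is a normal choice for describing toxicity, and adding unirradiated patients dilutes it. That supports the set for the descriptive tables, not for a test presented as a comparison of the arms.

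Table 1 will show how many patients were excluded and why, and survival is analysed in all randomised patients. Neither recovers non-fatal events in those excluded. Finally, BSC patients may receive radiotherapy after day 30, so the day-90 contrast is blurred whichever set is used. That is a separate issue and does not justify the filter at either time point.

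**Conclusion.** The concern holds. The filter acts on one arm, departs without explanation from Protocol 10.1.1, and governs the only planned test of a secondary harm endpoint. The wording of the set is certain; its effect on the result is not. If every RT+BSC patient was irradiated, there is none. With one or two exclusions it is small: the false-positive rate does not exceed 6.6% on the stated assumptions. Serious distortion, up to about 9 points and 10.9%, needs four or five exclusions with an event rate far from that of the irradiated patients. Direction and size cannot be settled from the documents. This should be fixed because the remedy is cheap, not because a large bias has been shown.

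**What to change.** Run the Table 30 CMH test on All Randomized Patients, analysed as randomised, a set SAP section 6 already defines. Keep All Treated for the descriptive and radiotherapy-related tables (29 and 31 to 35) and, if wanted, for a supportive version of Table 30. Reporting the number of unirradiated RT+BSC patients beside it would show whether the filter mattered.

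State one rule, the same in both arms, for patients with no day-30 or day-90 adverse event report, and reconcile it with the assessed-patients restriction in Protocol 14.2. Fix the rule before the data are seen, because it can matter as much as the filter. As an assumed example, with 3 RT+BSC and 6 BSC patients lacking a report, counting them as event-free moves the difference (RT+BSC minus BSC) by (6 − 3) × p/33, which is +3.6 points at p = 40% and +5.5 points at p = 60%.

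The cost is a change of SAP wording, one counting rule and the reprogramming of one table; follow-up of all randomised patients is already planned. Table 30 could then have different denominators from Table 29, which a footnote can explain. Unirradiated patients would slightly dilute radiotherapy toxicity in Table 30, but radiotherapy-related events remain visible in Table 31.

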## 7. Statistical Analysis

### 7.1 General Methods

All comparisons between treatment arms will be carried out using a two-sided test at an alpha level of 5% unless otherwise specified.

When appropriate, discrete variables are summarized with the number and proportion of subjects falling into each category, and compared using Fisher's exact test. Continuous and ordinal categorical variables are summarized using the mean, median, standard error, minimum and maximum values and when appropriate, compared using the Wilcoxon test.

Percentages given in the summary tables will be rounded and may therefore not always add up to exactly 100%. Listings, tabulations, and statistical analyses will be carried out using the SAS (Statistical Analysis System, SAS Institute, North Carolina, USA) software.

Unless otherwise specified, date of randomization and stratification factors will be taken from the Centralized Randomization File.

Baseline evaluations will be those collected on CRF Eligibility Worksheet and Baseline Report and closest to, but no later than, the first day of study treatment for treated subjects and closest to, but no later than, the date of randomization, for subjects who were randomized but who never received treatment.

Laboratory results, adverse events, and other symptoms are coded and graded using the CTCAE Version 4.0 Criteria.

